9.2 SAMPLE SIZE DETERMINATION

This is a pilot study, with the purpose of discerning parameter estimates for use in powering a subsequent multi-center clinical trial. To estimate statistical power for this pilot design, we consider a comparison of outcomes by group across time. Previous studies have not examined the knee extension moment limb symmetry index, therefore the difference in knee joint position and the knee extension moment will be employed as proxy variables in order to estimate statistical power for this pilot design. We considered a comparison of outcomes between pre- and post-intervention^{17,18} and side-to-side differences in ACL-R patients. (Table 4).¹⁵

Using 2-sided testing between groups based on previous results, we will need 14 patients overall randomized at 1:1 ratio assuming 80% power to detect a significant difference in the knee extension moment between the groups with $\alpha=0.05$.¹³ Therefore, with recruitment of 40 subjects (goal of retaining 30

Table 4: Sample Size Calculations (N=sample size per group)

	Pre-intervention	Post-intervention	Sample Size
Peak Knee Extension Moment ¹⁰	3.7 ± 0.9	2.4 ± 0.5	N=7
Peak Knee Flexion ¹⁸	88.8 ± 8.0	105.0 ± 5.6	N=5
	Control	Intervention	Sample
Knee Flexion Angle ¹⁸	83.5 ± 20.5	103.8 ± 16.3	N=15
Vertical ground reaction force ¹⁸	2.0 ± 0.4	1.6 ± 0.3	N=14

subjects through study completion), we are adequately powered to declare significance. Thus, while not the primary purpose of this experiment, we are adequately powered to declare significance between groups.

9.3 POPULATIONS FOR ANALYSES

The following populations will be included in the statistical analysis:

- Modified Intention-to-Treat Analysis Dataset (participants who completed at least 50% of the intervention visits in the Biofeedback Arm of the study and who attended at least one of the post-intervention assessment visits)
- Safety Analysis Dataset: defines the subset of participants for whom safety analyses will be conducted (participants who completed at least intervention visit)
- Per-Protocol Analysis Dataset: defines a subset of the participants in the full analysis (ITT) set who complied with the protocol sufficiently to ensure that these data would be likely to represent the effects of study intervention according to the underlying scientific model (participants who completed at least 80% of the study intervention visits)
- Other Datasets that may be used for sensitivity analyses

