9 STATISTICAL CONSIDERATIONS

9.1 STATISTICAL HYPOTHESES

All statistical analysis will be completed under the direction of [name]. Depending on the outcome, change (completion-baseline), or the value at completion will be assessed, and the statistical significance of the group differences can be assessed by a t-test or the non-parametric equivalent (2-sample Wilcoxon). Standardized differences will be calculated for the purposes of powering the subsequent clinical trial.

- **Primary Efficacy Endpoint(s):**
We will test the hypothesis that our biofeedback program will decrease the risk of secondary ACL injury by improving loading and movement symmetry (knee extension moment asymmetry) during the dynamic task of landing from a jump 6 weeks post intervention.

Movement and loading symmetry will be assessed using the limb symmetry index ($LSI = \frac{ABS[Surgical] - ABS[Nonsurgical]}{0.5(ABS[Surgical] + ABS[Nonsurgical])} * 100$)^{2,3,7,34} prior to (baseline) and at two time points following (immediately following training (efficacy), and 6 weeks after (durability)) the biofeedback training program.

- **Secondary Efficacy Endpoint(s):**
No hypothesis testing will be completed for the secondary endpoint as this is a pilot clinical trial and will be used to determine the best procedures to following when planning a subsequent multi-center clinical trial. Therefore, we will demonstrate our ability to recruit 40 ACL reconstructed patients and assess study retention and compliance.

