9.4.2 ANALYSIS OF THE PRIMARY EFFICACY ENDPOINT(S)

The goal of the proposed study is to determine the impact of an innovative biofeedback training program on decreasing risk factors for secondary ACL injuries in adolescent athletes. Based on

previous work, the primary variable of interest and a surrogate for secondary ACL injury risk will be the knee extension moment limb symmetry index (LSI). The previously established movement asymmetry risk factors³² and therefore the primary measures of interest are the knee extension moment, vertical ground reaction force, and frontal plane knee range of motion. Symmetry between the operative and non-operative limbs in this study will be determined by calculating the limb symmetry index (LSI). Asymmetry in the peak knee extension moment has been identified as significant predictors of secondary ACL injuries (therefore reduction in this asymmetry will decrease the risk for secondary ACL injuries).³²

For **Aim 1** of this pilot study a within subject repeated measures assessment (ANOVA), as implemented under mixed models, will be used to determine if a clinical (LSI>90%) and/or statistical difference exists between the pre- and the two post-intervention time points (efficacy and durability) for the primary outcome of interest (knee extension moment asymmetry). Post-hoc testing will be completed for any variable that is determined to be statistically different.

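### Both defined efficacy sets select on attendance, the modified ITT rule is written for the biofeedback arm only, and no set is assigned to the primary endpoint

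*Combined protocol and SAP*

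**What the plan says.** Section 9.3 lists two efficacy sets and a non-specific entry for other datasets in sensitivity analyses.

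- **Modified ITT:** "participants who completed at least 50% of the intervention visits in the Biofeedback Arm of the study". A second condition asks for outcome data from one or both follow-up assessments. The attendance condition names one arm. Nothing is said about attendance among controls, who have six sessions of their own (section 6.1.1), or about how controls qualify for the set.
- **Per-protocol:** this "defines a subset of the participants in the full analysis (ITT) set who complied with the protocol sufficiently", made concrete as "participants who completed at least 80% of the study intervention visits". No arm is named. The ITT set it refers to is not separately defined and may simply be the modified ITT set.

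For the primary endpoint, section 9.4.2 says "a within subject repeated measures assessment (ANOVA), as implemented under mixed models, will be used". Section 9.1 plans between-group tests and adds: "Standardized differences will be calculated for the purposes of powering the subsequent clinical trial". Neither section names an analysis set.

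Three other sections determine which outcomes exist. Section 7.1 keeps people who stop the intervention in the study procedures. Section 7.2 allows the investigator to withdraw participants for significant non-compliance, or for being unable to attend sessions over a period printed as 2 days/weeks, and replaces those withdrawn after receiving the intervention. Section 5.5 only encourages people who withdraw to complete assessments.

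**The concern.** Attendance is observed after randomisation. A filter on attendance in one arm means the two groups compared are no longer the two groups randomised. If attendance is related to outcome, the between-group difference then carries a selection component that has nothing to do with the intervention. The same filter decides whose change is averaged in the pre-to-post analysis of 9.4.2.

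This matters even in a pilot, because section 9.2 describes the study as one "with the purpose of discerning parameter estimates for use in powering a subsequent multi-center clinical trial". The between-group standardized difference is a main product of the trial. With no set assigned to the primary endpoint, the choice between two attendance-selected sets and unspecified others could also be made after the data are seen.

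**Working it through.** The plan gives no figure of its own on this point, so there is nothing to reproduce. The check has four parts.

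**1. Cut-offs.** With 12 biofeedback sessions (9.4.3), 50% is 0.5 × 12 = 6, so the modified ITT set excludes anyone attending 5 or fewer. Per-protocol: 0.8 × 12 = 9.6, so 10 sessions; for controls, if the rule applies to them, 0.8 × 6 = 4.8, so 5.

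**2. Shift under no true effect.** From the documents: 20 per arm (4.1). Assumed, because the documents give neither: the number k of biofeedback participants below the cut-off, and the correlation r between attendance and outcome. All 20 controls are taken to enter unfiltered. If attendance and outcome are bivariate normal and the lowest fraction q = k/20 is removed from one arm, the large-sample shift in that arm's mean is r × φ(z_q)/(1 − q), in SD units.

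- k = 1, q = 0.05: φ = 0.1031, so r × 0.1031/0.95 = 0.022 (r = 0.2) to 0.054 (r = 0.5).
- k = 2, q = 0.10: φ = 0.1755, so r × 0.1755/0.90 = 0.039 to 0.098.
- k = 5, q = 0.25: φ = 0.3178, so r × 0.3178/0.75 = 0.085 to 0.212; at r = 0.3, 0.127.

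Simulation at 20 per arm (40,000 replicates, pooled t-test, two-sided 5%) agrees:

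| Removed | Mean standardized difference, r = 0.2 to 0.5 | Type I error |
|---|---|---|
| 1 | 0.02 to 0.05 | 5.1% to about 5.5% |
| 2 | 0.04 to 0.09 | about 5.2% to 6% |
| 5 | 0.09 to 0.21 | 5.7% to 9.3% |

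At r = 0 there is no shift. At r = −0.3 with 5 removed it is −0.13. The biofeedback arm's mean pre-to-post change moves by about 0.02 to 0.20 SD of change over the same range.

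For scale, the standard error of a standardized difference under no effect is √(1/n₁ + 1/n₂): √(2/20) = 0.32 at 20 per arm. Section 9.2 says "with recruitment of 40 subjects (goal of retaining 30"; 15 per arm gives √(2/15) = 0.37.

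**3. How much an all-randomised set would recover.** It can restore only participants who have outcomes. Let s be the shift with 5 of 20 removed. The 15 kept average +s, so the 5 removed average −3s. If m of the 5, taken at random, have outcomes and are put back, the remaining shift is (15s − 3ms)/(15 + m) = 3s(5 − m)/(15 + m). With r = 0.3, s is 0.12 to 0.13, and the remainder is:

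- m = 0: 0.12 to 0.13
- m = 1: 0.09 to 0.10
- m = 2: 0.06 to 0.07
- m = 3: 0.04
- m = 4: 0.02
- m = 5: 0

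The likely m is unknown. At two sessions a week for six weeks, missing at most one session a week loses at most 6. Anyone below the cut-off has missed at least 7, and so has missed both sessions in at least one week. On one reading of the 7.2 attendance criterion, most low attenders could therefore be withdrawn.

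**4. If biofeedback works.** Suppose 5 of 20 low attenders gain nothing and the other 15 gain δ, with r = 0. The all-randomised mean effect is (15/20)δ and the attendance-restricted one is δ, a gap of 0.25δ: 0.125 SD at an assumed δ of 0.5 and 0.25 SD at 1.0. This is a change in the quantity estimated as well as selection.

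**Planning consequence (illustration).** For 80% power, n per arm is about 2(1.96 + 0.84)²/d² = 15.68/d². An assumed true difference of 0.50 gives 63 (64 with the t correction). A +0.12 shift, to 0.62, gives 41 (42 with the correction). A negative shift would enlarge the next trial instead.

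**The case against.** The strongest reply is that little may be lost. Participants below 50% attendance may mostly be withdrawn under 7.2 and have no post-intervention assessment, in which case no choice of set recovers them. With one or two such participants the shift is at most about 0.09 SD. The larger figures need 5 of 20 low attenders and r near 0.5, and the documents support neither value. Section 9.2 says significance is not the main purpose, and 9.4.9 promises a caution on any significant result. A pilot may also legitimately want the effect among people who received a minimum amount of the intervention. Finally, modified ITT is listed first and is plausibly the parent of the per-protocol set, so the missing assignment is partly a drafting gap.

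Much of this stands as a limit on size and certainty. It does not justify an attendance rule stated for one arm only, nor leaving the primary endpoint without a named set. Interest in a minimum-attendance effect supports a secondary analysis, not the main one.

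A reader might infer that outcomes certainly will be collected and then discarded from one arm. The text does not establish that: 9.3 does not say how controls enter the set, and withdrawal under 7.2 is discretionary and its attendance criterion ambiguous.

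**Conclusion.** The defect in wording is certain: the modified ITT attendance rule covers the biofeedback arm only, the other defined efficacy set also selects on attendance, and no set is tied to the primary endpoint. It should be fixed.

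The consequence is conditional. It needs controls to enter unfiltered, some low attenders to have outcomes, and attendance to be related to outcome. Under the assumed inputs with no true effect, the shift runs from 0.02 to 0.21 SD, below one standard error throughout. It is nevertheless systematic and passes into the planning estimate.

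Two stronger readings are not supported. One is that the bias favours biofeedback: low attenders could be recovering worse or better, so the sign is unknown. The other is that these figures are an upper limit: they hold only with no true effect, and the gap can be larger if the intervention works.

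**What to change.** - In 9.3, define the primary efficacy set as all randomised participants in their assigned arm, using every available protocol assessment regardless of sessions attended. State that withdrawn and replaced participants with data stay in it.
- Name that set in 9.1 and 9.4.2.
- Report by arm how many participants have no post-intervention assessment.
- Apply any attendance-based sets (50%, 80%) to both arms, and keep them as supporting or sensitivity analyses only.

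The cost is wording in 9.1, 9.3 and 9.4.2, plus a note beside the planned 40 (20 per arm) that the randomised set may exceed 40 when participants are replaced. No new data are needed, and enrolment and withdrawal rules are untouched. The downside is that the estimate will include non-attenders and may be smaller. Selection from missing outcomes remains, which is why the counts by arm are needed.

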9.4 STATISTICAL ANALYSES

9.4.1 GENERAL APPROACH

- For descriptive statistics the results will be reported as percentages as well as means and standard deviations as appropriate for the measure. Categorical data will be reported as percentages while continuous data will be reported as means with standard deviations as well as data ranges.
- For inferential tests, indicate the p-value and confidence intervals for statistical significance (Type I error) and whether one or two-tailed.
- Checks for the assumption of normality will be performed prior to additional statistical procedures. If this assumption is not met then corrective procedures will be applied such as transformation or nonparametric tests as appropriate.

9.4.2 ANALYSIS OF THE PRIMARY EFFICACY ENDPOINT(S)

The goal of the proposed study is to determine the impact of an innovative biofeedback training program on decreasing risk factors for secondary ACL injuries in adolescent athletes. Based on

previous work, the primary variable of interest and a surrogate for secondary ACL injury risk will be the knee extension moment limb symmetry index (LSI). The previously established movement asymmetry risk factors³² and therefore the primary measures of interest are the knee extension moment, vertical ground reaction force, and frontal plane knee range of motion. Symmetry between the operative and non-operative limbs in this study will be determined by calculating the limb symmetry index (LSI). Asymmetry in the peak knee extension moment has been identified as significant predictors of secondary ACL injuries (therefore reduction in this asymmetry will decrease the risk for secondary ACL injuries).³²

For **Aim 1** of this pilot study a within subject repeated measures assessment (ANOVA), as implemented under mixed models, will be used to determine if a clinical (LSI>90%) and/or statistical difference exists between the pre- and the two post-intervention time points (efficacy and durability) for the primary outcome of interest (knee extension moment asymmetry). Post-hoc testing will be completed for any variable that is determined to be statistically different.

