8.2 SAFETY AND OTHER ASSESSMENTS

Following recruitment and the completion of informed consent, each subject will be asked to complete an initial biomechanical assessment in the Kevin P. Granata Biomechanics Lab at Virginia Tech. All subjects will be asked to wear form fitting shorts and a shirt, plus a pair of athletic shoes (Nike Pegasus, Nike Inc, Beaverton, CO) all of which will be provided for them to use during testing (Figure 2). Previous literature has shown that differences in footwear can alter the ground reaction forces.^{35,38} Therefore in a between-subject design comparing two

groups (Aim 1) it is important to alleviate any potential differences due to footwear. Patients will warm up by cycling on a stationary bike at a comfortable pace for 5 minutes. The seat height for the bike will be standardized for all subjects so that when the leg is fully extended at the bottom of the pedal stroke there will be between 5 and 10 degrees of knee flexion. The seat settings will then be recorded on the data collection sheet and entered into REDCap in order to ensure that the same seat settings are used at each visit. After the warm-up, patients will have retro-reflective markers attached at specific locations on both lower extremities to track segmental motion during both squatting and landing. Three-dimensional coordinate data will be collected using a 10-camera motion capture system at a sampling rate of 120 Hz (Qualysis, Sweden). Ground reaction forces will be collected using 2 embedded force plates at a sampling rate of 2400 Hz (AMTI, Watertown, Massachusetts). Each subject will be asked to complete a standing trial followed by a series of squatting and landing trials as described below:

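### The primary analysis in 9.4.2 tests change over time only and omits the between-arm comparison on which 9.1, 9.2 and 8.2 rely

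*Combined protocol and SAP*

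**What the plan says.** **9.4.2 (primary efficacy analysis).** For Aim 1, "a within subject repeated measures assessment (ANOVA), as implemented under mixed models, will be used to determine if a clinical (LSI>90%) and/or statistical difference" is present. The difference sought is one that "exists between the pre- and the two post-intervention time points (efficacy and durability"), and post-hoc tests follow. Arm is not mentioned.

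**9.1 (hypotheses).** Either change or the value at completion may be analysed, and "the statistical significance of the group differences can be assessed by a t-test or the non-parametric equivalent (2-sample Wilcoxon"). The hypothesis concerns symmetry "during the dynamic task of landing from a jump 6 weeks post intervention". The two follow-up assessments are described as "immediately following training (efficacy), and 6 weeks after (durability").

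**9.2 (sample size).** The calculation is introduced with "Using 2-sided testing between groups based on previous results" and ends by claiming adequate power between groups. Its inputs are described differently: "We considered a comparison of outcomes between pre- and post-intervention". In Table 4 the knee extension moment row has pre- and post-intervention columns. Only the knee flexion angle and vertical ground reaction force rows have control and intervention columns.

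**8.2.** The footwear rationale for Aim 1 begins "Therefore in a between-subject design comparing two" groups.

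**4.2.** The attention control was chosen to limit a group difference caused merely by extra contact with the study team.

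**9.3.** The modified intention-to-treat set requires half of the intervention visits in the biofeedback arm. It gives no matching attendance rule for controls.

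**6.1.1.** Usual medical care continues in both arms.

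**The concern.** The trial randomises patients to biofeedback or attention control, yet the section that fixes the primary test compares time points, not arms. An analyst who follows 9.4.2 would fit a time effect, either pooled over both arms or in the biofeedback arm alone. Either can be significant because patients recover during 12 weeks of usual care. Neither uses randomisation to isolate the effect of biofeedback.

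The alternative in 9.1 does compare arms, but only permissively, and it leaves the form of the outcome open. Change or completion value, t-test or Wilcoxon, immediate or week-12 visit, time effect or arm effect can all be chosen after the data are seen. The primary result would then not be fixed in advance, and the power claim in 9.2 would attach to a different test from the one in 9.4.2.

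**Working it through.** **1. The sections side by side**

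| Section | Comparison | Visit | Form of outcome |
|---|---|---|---|
| 9.4.2 | baseline against follow-up, within subject | both | LSI over time, plus an LSI>90% criterion |
| 9.1 | between arms, optional wording | hypothesis names 6 weeks after the intervention; the efficacy label is on the immediate visit | change or completion value |
| 9.2 | between arms, two-sided | not stated | proxy variables, not the LSI |
| 8.2, 4.2 | between arms | not stated | not stated |

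No section ranks one above another.

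**2. Which test the sample size belongs to**

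Inputs are the means and SDs in Table 4, 80% power and two-sided alpha 0.05 (9.2). Formulas: pooled SD = √[(SD₁² + SD₂²)/2] and d = difference / pooled SD. The size per arm comes from the two-sample t-test (noncentral t). For the knee extension moment, pooled SD = √[(0.81 + 0.25)/2] = 0.728 and d = 1.3/0.728 = 1.79.

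| Table 4 row | Column headings | d | Computed n per arm | Printed N |
|---|---|---|---|---|
| Peak knee extension moment | pre/post | 1.79 | 6.05 | 7 |
| Peak knee flexion | pre/post | 2.35 | 4.08 | 5 |
| Knee flexion angle | control/intervention | 1.10 | 14.09 | 15 |
| Vertical ground reaction force | control/intervention | 1.13 | 13.30 | 14 |

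All four printed sizes reproduce after rounding up. A paired calculation for the knee moment gives 8, 6, 6 and 5 pairs at assumed pre/post correlations of 0, 0.3, 0.5 and 0.7, never 7. The sizing is therefore for a between-arm test, although the primary variable's effect size comes from pre/post columns.

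**3. What the time test does when biofeedback has no effect**

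The documents give no mean, SD, reliability or recovery rate for the LSI, so these inputs are assumed: ratio LSI with mean 80 and SD 20, and reliability r from 0.6 to 0.9. Each visit's score is a true score (variance 400r) plus independent error (variance 400(1−r)). There are three visits, 20 patients per arm and 4,000 replicates per cell. The table gives the proportion of trials significant at 0.05, as a range over r.

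| Scenario, same in both arms | Time test, pooled n=40 | Time test, one arm n=20 | Baseline-adjusted arm difference, week 12 |
|---|---|---|---|
| No recovery, no selection | 5%–6% | 5% | 4%–6% |
| 2 points of recovery | 10%–29% | 7%–16% | 4%–6% |
| 5 points of recovery | 42%–96% | 21%–71% | 4%–6% |
| Entry only below 90 on a ratio scale, no recovery | 10%–30% | 8%–16% | 4%–6% |

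A second calculation on change scores assumed equal improvement of 0.3 to 0.8 SD, pre/post correlation of 0.5 to 0.7 and 15 per arm. It gave 19% to 96% for the biofeedback arm alone, 36% to 100% pooled, and about 5% between arms.

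**4. The entry cut-off**

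The last row of that table applies only if the 90% cut-off (5.2, criterion 16) is on a ratio scale. The printed formula is (S − N)/[0.5(S + N)] × 100, where S and N are the absolute surgical and nonsurgical values. It equals 0 at symmetry. At S/N = 0.8 it is −0.2/0.9 × 100 = −22. A value of 90 needs S/N = (1 + 0.45)/(1 − 0.45) = 2.64. On that scale the cut-off would exclude almost nobody, and the LSI>90% criterion in 9.4.2 would not mean symmetry.

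**5. What the between-arm test can detect**

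- 80% power needs d = 1.06 with 15 per arm (the retention goal) and d = 0.91 with 20 per arm.
- With 15 per arm, power is 83% for d = 1.10 and 85% for d = 1.13, the two control/intervention rows.
- For an assumed 10-point effect at reliability 0.75, the adjusted standardised difference is 10/[20√(1 − 0.75²)] = 0.76. Simulated power for the arm difference is about 60% to 63% with 20 per arm and about 50% with 15 per arm. The pre/post test within the biofeedback arm (n=20) has about 89%.

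**The case against.** The strongest reply is that 9.4.2 is under-specified rather than wrong. It invokes mixed models, 9.2 speaks of outcomes by group across time, 9.1 names a two-sample test and 4.2 justifies a control arm, so a sensible reader would expect arms to be compared. That is a fair guess at intent. But 9.4.2 says within subject and lists only time points, and nothing gives another section precedence.

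A second reply is that this is a pilot. Section 9.2 says that declaring significance is not its main purpose, and 9.4.9 promises a cautionary note on significant findings. That lowers the stakes. Even so, 9.4.9 tests the primary outcome at 0.05 and 9.2 claims power to declare significance between groups.

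Several narrower points stand:

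- Section 9.1 separately plans standardised differences for the next trial, so a pre/post primary analysis would not remove them. It does not say at which visit or on which form of the outcome.
- The simulated error rates rest on no trial data. They show direction and mechanism only, and 2.2 says deficits can persist for up to two years.
- The deciding visit is less open than the test, because 4.1 and 9.1 both place the hypothesis at 6 weeks after the intervention. The efficacy label on the immediate visit, and the goal in 2.2 of an immediate effect that is then retained, still conflict with that.
- The remark in 8.2 is about footwear, so it is indirect evidence.
- The analysis-set and LSI-formula problems are separate defects and do not make this one more serious.

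**Conclusion.** The concern holds and must be fixed. The conflict is textual and needs no assumption: the primary-analysis section specifies a time comparison, the rest of the plan presumes an arm comparison, and nothing settles which test or visit decides. Table 4 confirms that the sample size belongs to the arm comparison.

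The size of the resulting bias is unknown because no recovery rate is documented. Under the assumed inputs, a true null gives a significant pooled time effect in anything from about 5% of trials with no recovery to 96% with 5 points of recovery at reliability 0.9. The arm difference stays at 4% to 6% throughout. Regression to the mean would add to the bias only if the entry cut-off is on a ratio scale, which the printed formula contradicts.

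**What to change.** **Changes**

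1. In 9.4.2, specify a linear mixed model with arm, visit and arm-by-visit terms, or a baseline-adjusted arm difference. Make the between-arm difference in knee extension moment LSI at one named visit the primary test, at two-sided alpha 0.05.
2. Say which visit decides. Week 12 matches the hypothesis in 4.1 and 9.1, but the efficacy label sits on the immediate visit, so one of the two must change. The other visit becomes secondary, and within-arm pre/post changes become descriptive.
3. In 9.1, replace the optional wording and the choice between change and completion value with this test. Say which contrast and visit the standardised differences refer to.
4. In 9.2, state the power for this contrast, and say that the knee extension moment row uses a pre/post difference as a proxy.
5. In 9.3, define the analysis set so that both randomised arms enter by the same rule.
6. Reconcile the printed LSI formula with the 90% criteria in 5.2, 8.2 and 9.4.2.

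**Cost**

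These are text changes to 9.1 to 9.3 and 9.4.2 and to the LSI wording, with no new visits or data. N=40 need not change on the plan's between-arm inputs, although neither of those rows is the primary endpoint. The price is a contrast less likely to reach significance: for the assumed 10-point effect, about 60% to 63% power with 20 per arm and about 50% with 15, against 89% for pre/post change in one arm of 20.
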